3 OBJECTIVES AND ENDPOINTS

3.1 1-MONTH PRIMARY ENDPOINT

The primary 1-month endpoint is defined in terms of an event rate, and includes technical failure and any of the following:

- *Severe Bowel Ischemia* – lack of adequate blood flow to the intestines leading to surgical/endovascular intervention or death and reported within 30 days of the index procedure
- *Permanent Paraplegia/Paraparesis* – event reported within 30 days of the index procedure without resolution at 30 days post-procedure
- *Renal Failure* – new onset renal failure requiring dialysis that remains on-going at 30 days post-procedure
- *Disabling Stroke* – new neurological deficit resulting from vascular insult reported within 30 days of the index procedure without resolution at 6 months post-procedure. Disabling is considered a value of 2 (slight disability) or above on the modified Rankin Scale (mRS) at both the 1-month and 6-month visits.
- *Abdominal Aortic Aneurysm Rupture* - Intraoperative and Post-procedural rupture through the aneurysm wall within the stented segment of the aorta reported within 30 days of the index procedure.
- *Aneurysm-related mortality* - death reported within 30 days of the index endovascular procedure

The technical success component of the endpoint (counterpart to technical failure) is defined as:

- a. Successful access and delivery of all ChEVAS components (i.e., ability to deliver each component to the intended location, without the need for unanticipated corrective intervention related to delivery);
- b. Successful and accurate deployment, defined as:
 - i. Deployment of the Nellix stent-grafts, Ovation limbs, and chimney(s) in the planned location;
 - ii. Patency of the Nellix stent-grafts, Ovation limbs, and chimney(s) with absence of device deformations (e.g., kinks¹, mal-deployment², misaligned deployment³) requiring unplanned placement of an additional device within the endovascular stent-grafts or chimney(s);
 - iii. Adequate seal without the need for unanticipated corrective interventions⁴. No use of components outside the defined ChEVAS System for the purpose of achieving seal. The use of adjunctive stenting for purposes outside of achieving seal or use

¹ Defined as a focal narrowing of the stent lumen of >50%, with concurrent stent wall deformation at that location.

² Defined as concluding the procedure without having all components of the ChEVAS System successfully deployed.

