³ Defined as, at the conclusion of the procedure, a > 10mm difference between the top of the Nellix stents, or the top of a visceral stent being > 14mm below the Nellix stent (the bag shelf is 4mm below the top of the Nellix stents).

⁴ Concomitant procedures, including those for infrequently encountered circumstances, may be anticipated and prepared for as part of a comprehensive endovascular approach

of adjunctive stents that are part of the defined system, does not result in technical failure.⁵

- c. Successful withdrawal (i.e., successful withdrawal of the delivery systems without the need for unanticipated corrective intervention related to withdrawal).

Multiple events occurring to a subject are considered a single subject failure for the purposes of calculating the composite one-month rate, as the rate is based on the total number of subjects. Since none of these variables are restricted by imaging requirements for detection, the cutoff date for the endpoint is exactly 30 days from the index procedure.

3.2 1-YEAR PRIMARY ENDPOINT

The primary 1-year endpoint is a blend of safety and effectiveness indicators. The endpoint is defined as the absence of:

- Abdominal aortic aneurysm rupture (0 - 365 days);
- Aneurysm-related mortality (0 – 365 days)
- Imaging-determined events at the 12-month imaging window. These do not require an intervention within 12 months to count as events:
 - Type I or Type III endoleak
 - Migration⁶ > 10mm
 - Sac Expansion⁷ > 5mm
 - Loss of Patency (100% occlusion) in Branches⁸, Nellix, or iliac limbs not seen at the index procedure
- Open conversion through day 365

⁵ Examples of acceptable procedures include:

- Placing an additional stent (Verta or Lifestent) to correct kink in visceral vessel (or a kink in the stent resulting from the vessel anatomy) or to smooth transition from Verta to visceral vessel (transition stenting)
- Placing an additional stent (Verta or Lifestent) to treat pre-existing visceral artery stenosis (spot stenting)
- Placing Verta stent within initial Verta stent due to length discrepancy, need to achieve a Verta length not covered by available lengths, or inadequate initial seal
- Placing Ovation limb to extend Nellix in order to obtain an adequate distal seal;
- Coiling of non-treated branch vessels
- Ballooning of any vessel or stent

⁶ As measured by the proximal end of the Nellix stents relative to the reference artery

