8 STUDY ASSESSMENTS AND PROCEDURES

8.1 SCREENING

The site begins the screening process by obtaining informed consent from the patient. The site must ensure they are using the correct IRB approved version of the informed consent and are following their informed consent process. After obtaining informed consent for the patient, the site records the informed consent date in the Electronic Data Capture System (EDC), and then completes the inclusion/exclusion CRF page (this might also involve a serum pregnancy test if the subject is a female of childbearing potential). The site then submits the patient's CTA to the Core Lab, which can be done either electronically, or via mail. The site may now enter the Demographics & Vascular Characteristics (including vitals and serum creatinine) and Medical History information into the EDC.

The Core Lab reviews the CTA for anatomical inclusion/exclusion criteria conformity. If the subject does not pass this step the subject is dropped from further consideration. If the subject passes Core Lab, the subject is referred to the Case Review Board (CRB) for further evaluation.

The CRB reviews the case for overall trial suitability. The CRB may also make procedural recommendations to the Site. If the CRB recommends the subject for the study, the subject is approved for implantation.

Reasons for subject exclusions (Core Lab or CRB), along with any CRB procedural recommendations, will be captured and reported.

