9 STATISTICAL CONSIDERATIONS

9.1 STATISTICAL HYPOTHESES

A formal Statistical Analysis Plan (SAP) has been created, thus these sections will present summaries. Please refer to the SAP for additional detail. The study evaluates two primary endpoints: a 1-month endpoint and a 1-year endpoint. Both these endpoints blend safety and effectiveness measures so they are not termed “Safety Endpoint” or “Effectiveness Endpoint.”

Primary 1-Month Endpoint

The primary 1-month endpoint for the ChEVAS Cohort is defined as an event rate, including technical failure, and the occurrence of severe bowel ischemia, permanent paraplegia/paraparesis, renal failure, disabling stroke, abdominal aortic aneurysm rupture, and aneurysm-related mortality within 30 days of the index procedure. The null and alternative hypotheses are defined below.

$$H_0: \pi \geq 25\% \text{ vs. } H_1: \pi < 25\%$$

where π is the event rate at 30 days for the study test group, and 25% is the 30-day goal. A univariate test utilizing the exact binomial distribution will be performed to determine if the frequency of the 30-day

composite endpoint is statistically significantly less than the performance goal of 0.25. This is discussed further in the SAP.

Primary 1-Year Endpoint

The primary 1-year endpoint is defined as freedom from abdominal aortic aneurysm rupture and aneurysm-related mortality through 1 year (day 365), freedom from imaging-related findings in the 1-year window (Type or III endoleak, migration > 10 mm, AAA sac expansion > 5 mm, and occlusion within the ChEVAS System not seen at the index procedure), and open conversions and other major device-related interventions through day 365. The primary 1-year analysis will compare the treatment success composite to a target performance goal of 75%. The null and alternative hypotheses are defined below.

$$H_0: \pi \leq 0.75 \text{ vs. } H_1: \pi > 0.75$$

where π = the proportion of treated patients who meet the Treatment Success definition. A univariate test will be performed to determine if the frequency of subjects who meet the treatment success definition is statistically significantly higher than the performance goal of 0.75. This is discussed further in the SAP.

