9.2 SAMPLE SIZE DETERMINATION

The number of patients enrolled into this study is driven by the performance goals, expected device performance, and requirements for the alpha error and power. Due to the decrease in number of evaluable subjects at 1 year, the size of the study is determined entirely by the 1-year primary endpoint. Given a minimum power requirement of 80%, alpha=0.05, target goal=75%, estimated 1-year performance of 85.7%, and the univariate binomial test plan, a minimum evaluable sample size of 103 is needed. Accounting for an approximate drop-out rate of 14%, 120 subjects would be needed to achieve the minimum power and alpha requirements. The 1-month endpoint assumes a target goal of 25%, estimated performance of 14.5%, and a similar univariate binomial test structure. Given that all 120 subjects will be analyzed for the primary 1-month endpoint, the 1-month endpoint has power of 85.6%. This is described further in the SAP.

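### Several technical-success criteria turn on whether a step was anticipated or planned, but the protocol requires no pre-procedure record of this and names no assessor

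*Combined protocol and SAP*

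**What the plan says.** Section 3.1 defines the 1-month primary endpoint as an event rate that includes technical failure. The delivery criterion (a) is met when components are delivered "without the need for unanticipated corrective intervention related to delivery". The seal criterion (b.iii) and the withdrawal criterion (c) also rest on the word *unanticipated*. Criterion b.i refers to the *planned* location, and b.ii to *unplanned* placement of a further device.

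Footnote 4, attached to b.iii, reads: "Concomitant procedures, including those for infrequently encountered circumstances, may be anticipated and prepared for as part of a comprehensive endovascular approach". It gives no time point, record or assessor.

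Section 8.1 does provide for a pre-procedure record of a kind. The Case Review Board (CRB) sees each case before implantation, and the reasons for exclusion, "along with any CRB procedural recommendations, will be captured and reported". The protocol says the CRB may make such recommendations, so they are optional, and section 3.1 does not refer to them.

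On the test, section 9.1 states that "25% is the 30-day goal" and that "A univariate test utilizing the exact binomial distribution will be performed". Section 9.4.2 leaves the detail of endpoint components and methods to the SAP.

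**The concern.** Whether a corrective step during the procedure counts as an event can depend on what the team expected beforehand. If that expectation is not written down before the procedure, nobody can check it later, and an analyst cannot rebuild the classification from the data. Footnote 4 makes this harder, because it extends anticipation to infrequent circumstances without a limit. By contrast, footnotes 1 and 3 set numeric thresholds for kinks and misalignment, and footnote 5 gives worked examples.

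The trial has a single treatment group tested against a fixed goal. A more generous reading of *anticipated* therefore moves the observed rate in one direction only, with no control group to absorb it.

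**Working it through.** **Inputs.** From section 9.2: "The 1-month endpoint assumes a target goal of 25%, estimated performance of 14.5%, and a similar univariate binomial test structure". The significance level comes from the 1-year calculation in the same section ("Given a minimum power requirement of 80%, alpha=0.05, target goal=75%, estimated 1-year performance of 85.7"%), since the 1-month test is described as similar. Section 9.2 also gives the target figure: "Given that all 120 subjects will be analyzed for the primary 1-month endpoint, the 1-month endpoint has power of 85.6"%. Sidedness is not stated in words; the alternative in 9.1 is directional (event rate below 25%).

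**Step 1: reproduce the plan's power.** Find the largest c with P(X ≤ c | n=120, p=0.25) ≤ 0.05.
- P(X ≤ 21 | 120, 0.25) = 0.0330
- P(X ≤ 22 | 120, 0.25) = 0.0534

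So c = 21. Power = P(X ≤ 21 | 120, 0.145) = 0.8556, which matches the stated 85.6%. At one-sided 0.025 the limit is 20 events and power is 0.792, which does not match. The plan's figure is therefore an exact binomial test at one-sided 0.05.

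**Step 2: the margin.** 21/120 = 17.5% passes with p=0.033. 22/120 = 18.3% fails with p=0.053. One subject's classification can decide the endpoint.

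**Step 3: sensitivity to relabelling.** Suppose the true event rate is 25% and a share d of all subjects is moved from event to non-event. The chance of a false pass is P(X ≤ 21 | 120, 0.25 − d). The values of d are assumptions; the documents give none.

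| d (percentage points) | Average subjects (120 × d) | Chance of false pass |
|---|---|---|
| 0 | 0 | 0.033 |
| 1 | 1.2 | 0.056 |
| 2 | 2.4 | 0.090 |
| 3 | 3.6 | 0.139 |

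**Step 4: do the existing safeguards cover this?**
- *CEC (10.1.5).* It reviews endpoint events independently, but the adverse events it adjudicates are those the study team identifies. Technical failure is not among the listed examples. A corrective step within the index procedure would not be a secondary procedure, which section 8.5.11 defines as coming after it.
- *Source verification (10.1.6).* It is complete for primary endpoints, but cannot verify an expectation that was never recorded.
- *Index Procedure CRF (8.4).* It lists concomitant procedures performed. No field separating planned from unplanned steps is described.
- *CRB (8.1, 8.2).* It acts at the right time, but its recommendations are optional and not linked to section 3.1.

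**The case against.** The strongest reply is that most of the definition does not depend on the label. Bringing in a component from outside the system to obtain seal is a failure whatever was expected (b.iii), and so is an aborted procedure (7.1). Footnote 5 already accepts ballooning, a second Verta stent for inadequate initial seal and an Ovation limb for distal seal. Footnote 4 hangs on b.iii alone, so carrying it over to delivery and withdrawal is an inference from a shared word. It concerns concomitant procedures, which section 3.3.3 illustrates with items such as iliac conduits and patch repair. Its wording pairs anticipation with preparation, which most naturally means beforehand. All of this stands. It confines the problem to the remaining corrective interventions, but does not supply the missing record for them.

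A second reply is that the SAP or the CEC Charter may hold the rule. That is possible: the SAP's own text and the Charter are not in the material available here, and the CEC list is expressly open-ended. The absence of a rule is therefore established only for the protocol text. The endpoint definition should still contain the rule or point to it.

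A reader might infer that the operator can remove a primary event after the fact. The documents do not show this. No assessor of technical success is named, and independent review and source verification are both foreseen. The supportable statement is that the classification could not be verified afterwards.

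A reader might also try to size the gap by subtracting the largest registry's early death, stroke and dialysis rates in Table 3 (2.8 + 2.6 + 1.3 = 6.7%) from the planned 14.5%, leaving about 8 points for technical failure. That does not hold. Every series in Table 3, including that registry, reports 100% technical success. The stroke and dialysis rows do not use the endpoint's definitions. Adding the rates also treats the events as mutually exclusive.

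**Conclusion.** The concern holds in a limited form. For corrective interventions that are neither accepted by footnote 5 nor automatic failures, the protocol leaves *anticipated* and *planned* without a required record or a named assessor. How many subjects this touches cannot be estimated from the documents.

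The consequence is that a primary endpoint with a one-subject margin partly rests on a label that cannot be checked. The rise in false-pass risk from 3.3% to between 5.6% and 13.9% is conditional on a true rate of 25% and an assumed 1 to 3 points of relabelling. It is not a forecast. The calculation takes all 120 subjects as analysed and the test as one-sided at 0.05, which the reproduced power supports.

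**What to change.** In section 3.1, and in the SAP to match:

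1. State that, apart from the procedures accepted in footnote 5, a corrective intervention counts as *anticipated*, and a location or device as *planned*, only if it is recorded for that subject in the case plan before enrolment. The existing CRB form is a natural place.
2. Limit footnote 4 to procedures so recorded.
3. Add technical failure to the events the CEC adjudicates.

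Keeping the footnote 5 exemption matters. A blanket rule that every unlisted corrective step is a failure would turn steps the protocol already accepts into events, and so change the endpoint for which the 25% goal and the 14.5% estimate are stated.

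The cost is one form field, a few sentences and some extra CEC work. The planned 120 subjects need not change on this account, but stricter counting may raise the event rate. If the assumed 14.5% rises by one point, power is P(X ≤ 21 | 120, 0.155) = 0.772, down from 0.856. With two or three points it is 0.670 or 0.558. The sponsor should check whether the 14.5% estimate was obtained under the same definition.

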⁷ As measured across the maximum transverse sac diameter relative to the 1-month scan

⁸ Branches refer to stents in the left renal artery, right renal artery, and superior mesenteric artery

- Other major device-related⁹ surgical or endovascular re-interventions through day 365 for:
 - Type I or III endoleak, or gutters
 - Migration
 - Thrombotic events/Occlusions - complete loss of patency in any of the components of the ChEVAS System due to thrombotic events and/or device deformation
 - Device deformation resulting from fracture, that leads to clinical sequelae of vessel stenosis progressing to decreased perfusion, or puncturing of graft material leading to endoleak
 - Relining of the Nellix Stents to correct stenosis or kink
 - Mal-deployed device that leads to clinical sequelae of migration, endoleak, or thrombosis
 - Device infection

Non-major interventions are not included in the endpoint:

- Endovascular intervention for branch stenosis (within the stent or distal to the stent) for a reason other than stent fracture
- Interventions for Type II endoleaks
- Non endovascular treatments for procedural complications that are non-device specific, e.g., seroma, surgical site infection etc.

The 1-year endpoint is a collection of variables that may be detected at any time or require imaging to be detected. As such, variables are evaluated differently for the “1-year” timeframe. Variables lacking imaging restrictions (rupture, mortality, interventions) are evaluated until day 365 for the 1-year endpoint as the exact day of the event will be known. Onset dates for imaging-driven variables are unknown (they have may occurred at any time prior to the imaging scan that detected them) and thus are evaluated at the one-year imaging window as determined by the scan date. Presence of positive imaging-related findings within the 1-month or 6-month imaging windows does not factor into the endpoint analysis. Rather, the endpoint analysis restricts positive findings to only those within the 1-year imaging window. Imaging results used in the endpoint analysis will be sourced from core lab assessments.

In contrast to classic EVAR studies that analyze safety at 1 month and effectiveness at 1 year, the ChEVAS study is designed to evaluate both safety and effectiveness across dual endpoints (thus, passing both endpoints will indicate the trial has demonstrated safety and effectiveness).

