An external Core Lab will be used for this study. The Core Lab will be responsible for reading both screening and follow-up scans provided by the sites. Their findings and measurements will be recorded into the Electronic Data Capture (EDC) system. The results from the Core Lab will be used in the assessment for device-related findings, including endoleaks, aneurysm enlargement, gutters, kinking, and stent fractures. Occlusion will be primarily reported by the site due to a clinical finding (e.g., claudication) and confirmed via angiogram with the subject in the operating theater (i.e., utilizing CT scan results would under-report this event).

¹⁰ Secondary ChEVAS does not count as prior ChEVAS experience

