8.5.11 ADDITIONAL ADVERSE EVENT DEFINITIONS

Additional events or occurrences of interest that have relevance to the study device, therapy, disease, re-intervention or evaluations to be captured for endpoint analysis are as follows:

- *Abdominal Aortic Aneurysm Rupture* – intra-operative or post-procedural rupture through the aneurysm wall within the stented segment of the aorta
- *All-Cause Mortality* – Death from any cause
- *Aneurysm Related Mortality* – death reported within 30 days of the index endovascular procedure, due to aneurysm rupture, within 30 days of re-intervention or conversion to open repair, or as otherwise determined by the Clinical Events Committee
- *Aneurysm Sac Enlargement* – aneurysm sac diameter increase of >5mm in late follow-up as compared to the initial post-operative measurement (30 day follow-up)
- *Conversion to Open Repair* – open surgical repair of the abdominal aortic aneurysm due to unsuccessful delivery or deployment of the stent graft and/or renal stents, due to complications or other clinical situations that precluded successful endovascular treatment, or at any time

following initial successful endovascular treatment for any reason. Conversion to Open Repair shall always be captured as a re-intervention

- *Distal Ischemia* – New onset of compromised peripheral blood flow resulting in femoral or peripheral arteria occlusion or stenosis (attributable to the index procedure and not related to natural progression of atherosclerotic disease) causing a threat to the viability of the limb and requiring surgical or percutaneous intervention
- *Endoleak* – Clear evidence of contrast outside of one or both EndoBags, which communicates with the aneurysm sac
 - *Type Ia* – originating proximally at the infrarenal segment
 - *Type Ib* – originating distally
 - *Type Ic* – originating at a chimney stent (visceral vessel)
 - *Type II* – originating from a patent lumbar artery, inferior mesenteric artery, or other collateral visceral vessel
 - *Type III* – between components, if an extender is used
 - *Type IV* – trans-device
- *Gutters* – Clear evidence of contrast outside of one or both EndoBags, which does not communicate with the aneurysm sac
- *Implant Occlusion* – Radiological finding indicating 100% blockage of device lumen
- *Luminal Thrombus* – endograft thrombosis resulting in any endovascular or surgical intervention after completion of the Nellix system implantation

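### The 1-year endpoint takes occlusion from core-lab scans in Section 3.2 but mainly from site reports in Section 4.1, and the Type Ia endoleak definition does not match the ChEVAS seal zone

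*Combined protocol and SAP*

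**What the plan says.** **Occlusion.** Section 3.2 lists a new 100% loss of patency in the branches, Nellix or iliac limbs among the events determined by imaging in the 12-month window. It adds of these events: "These do not require an intervention within 12 months to count as events". It names the source: "Imaging results used in the endpoint analysis will be sourced from core lab assessments". It also sets aside positive findings at 1 and 6 months, because "the endpoint analysis restricts positive findings to only those within the 1-year imaging window". Table 4 puts that window at days 305 to 425. As a separate component, Section 3.2 counts major device-related re-interventions through day 365, including those for "complete loss of patency in any of the components of the ChEVAS System".

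Section 4.1 first gives the core lab a general remit: "The Core Lab will be responsible for reading both screening and follow-up scans provided by the sites". Its list of device findings to be taken from the core lab does not include occlusion. It then says: "Occlusion will be primarily reported by the site due to a clinical finding (e.g., claudication) and confirmed via angiogram", with the subject in theatre, and explains that "utilizing CT scan results would under-report this event".

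Section 8.5.11 defines implant occlusion as "Radiological finding indicating 100% blockage of device lumen" and does not name a reader. Section 10.1.5 sends endpoint events to the CEC but ranks no sources. Section 9.4.2 leaves components and methods to the SAP.

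**Type Ia endoleak.** Section 8.5.11 places Type Ia proximally at the infrarenal segment, Ib distally and Ic at a chimney stent. The Synopsis admits an infrarenal neck shorter than 10 mm, including 0 mm. The Synopsis and footnote 11 of Section 5.1 start the landing zone below the celiac, the SMA or the proximal renal artery, depending on which vessels are stented.

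**The concern.** Two sections name different main sources for one component of a primary endpoint, and one of them says the other's source would undercount. In a single-arm comparison with a fixed goal, a failing subject who goes uncounted becomes a success, and no control arm shares the error. If the rule is not settled before the data are read, the classification of such subjects may be decided after their results are known.

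The Type Ia wording raises a similar problem. The endpoint counts Type I leaks. Read literally, the definition has no category for a leak at the proximal seal that this device is designed to create.

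**Working it through.** **1. Which subjects are classified differently?**

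| Angiogram-confirmed 100% occlusion, new since the index procedure | Section 3.2 as written | Section 4.1 source |
|---|---|---|
| Re-intervened on by day 365 | Failure (re-intervention component) | Failure |
| Not re-intervened on, called on the core-lab 1-year scan | Failure (imaging component) | Failure |
| Not re-intervened on by day 365, not called on that scan | Success, if no other event | Failure, if this source feeds the endpoint |
| Treated after day 365 but before a scan as late as day 425, which then shows a patent lumen | Success, if no other event | Failure, if this source feeds the endpoint |

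The last row is a special case of the third: the treatment is too late for the re-intervention component and too early for the scan to show the occlusion.

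**2. The plan's own figures.** Inputs from Sections 9.1 and 9.2: goal 75% success (failure rate 0.25 under the null), expected success 85.7% (failure rate 1 − 0.857 = 0.143), alpha 0.05, 103 evaluable, 14% drop-out. The plan does not state whether alpha is one- or two-sided. An exact binomial test with one-sided alpha 0.05 reproduces it:

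- With X failures among 103, the test passes if X ≤ 18 (at least 85 successes).
- Size: P(X ≤ 18 | 103, 0.25) = 0.0456.
- Power: P(X ≤ 18 | 103, 0.143) = 0.855.
- From n = 103 upward, power stays at or above 80% at every n checked (to 249), which matches the stated minimum.
- Enrolment: 103 / (1 − 0.14) = 119.8, rounded up to 120.
- 1-month check: P(X ≤ 21 | 120, 0.145) = 0.856, as stated.

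One-sided 0.025 does not reproduce the plan: power would be 70.0% at 1 year and 79.2% at 1 month.

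**3. Sensitivity to missed failures.** The documents give no rate for the exposed group, so these are illustrations only, with the true failure rate at the null value of 25%.

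- One failing subject missed: P(X ≤ 19 | 103, 0.25) = 0.0742, against 0.0456.
- 0.1 percentage point missed on average: P(X ≤ 18 | 103, 0.249) = 0.048.
- 0.25 point missed: P(X ≤ 18 | 103, 0.2475) = 0.051.

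Table 3 reports graft occlusion of 3.0% and 6.25% in two series. Those are total rates. They do not say how many occlusions were untreated and also missed on CT, so they do not size the exposed group.

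**4. Effect of counting more failures.** If a fuller rule raises the failure rate by 1 point, from 14.3% to 15.3%, power is P(X ≤ 18 | 103, 0.153) = 0.778.

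**5. Type Ia.** Take a subject with a 0 mm infrarenal neck whose seal starts below the SMA. A leak into the sac at that seal is not at the infrarenal segment (Ia), not distal (Ib) and not at a chimney stent (Ic). Section 8.5.11 has no other Type I category.

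**The case against.** The best reply is that the two sections complement each other. The Section 4.1 sentence concerns symptomatic occlusions seen in theatre. Many of these would probably be treated there, although the text does not say so. A later CT would then under-report them because the vessel had been reopened, not because CT cannot show a blocked lumen. Section 3.2 already counts such cases through day 365 by the re-intervention component. On this view Section 3.2 governs the endpoint, Section 4.1 describes how occlusions come to notice, and the SAP may settle the rest.

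Much of this stands. A reader might infer that occlusions in general escape the endpoint, or that the protocol declares CT unfit to detect them. The documents support neither: treated occlusions have their own component, and most untreated ones should appear on the 1-year scan. Section 4.1 also states no endpoint scoring rule.

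What does not stand is that the text is already reconciled. Nothing available ranks the two sources, Section 4.1 leaves occlusion off its core-lab list, and an occlusion treated between day 365 and the scan escapes both components.

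On Type Ia, the reply is that Sections 2.3.3.1.1 and 2.3.4 use the term for leaks around chimney grafts, so a core lab would probably score a proximal leak as Type I. That is likely. It makes the definition a wording error and gives no ground for expecting such leaks to go uncounted.

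**Conclusion.** Both inconsistencies are real and should be corrected.

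For occlusion, the exposed group is narrow: an angiogram-confirmed occlusion, not re-intervened on by day 365 and not called on the core-lab 1-year scan, including one treated after day 365 but before that scan. The direction favours the device. The size is probably small and cannot be derived from the documents. The move from 4.6% to 7.4% assumes exactly one missed failing subject among 103 and a true failure rate of 25%. It is not an estimate, and smaller average losses barely change the figure. It would be wrong to infer that the sample size is in error, because it reproduces on the plan's own inputs.

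For Type Ia, the definition read literally does not cover the proximal seal. No numerical effect can be shown.

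The conclusion on occlusion is limited to the text available. The SAP may contain a source rule, but Sections 3.2 and 4.1 would still need to agree with it.

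**What to change.** 1. State one rule in both Sections 3.2 and 4.1. A new 100% occlusion is a failure if it is called on the core-lab 1-year scan, or if it is site-reported, angiogram-confirmed and CEC-adjudicated up to the date of that scan (day 365 if there is no scan), whether or not it was re-intervened on.
2. Say openly that this is an exception, for occlusion only, to Section 3.2's restriction to the 1-year imaging window. It changes a stated rule and is more than a cross-reference. Bring the summaries in the Synopsis and Section 9.1 into line, and name occlusion in the CEC Charter.
3. Confirm in the SAP that the 85.7% assumption and the 75% goal rest on the same occlusion rule.
4. In Section 8.5.11, define Type Ia as originating at the proximal seal zone (target landing zone) of the ChEVAS System.

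The cost is wording in the protocol, SAP and CEC Charter, plus adjudication of a few events; no new scans are needed. The statistical downside is that a few more failures may count. If 85.7% was set under the narrower rule and the failure rate is 1 point higher under the new one, power at 103 falls from 85.5% to 77.8%, below the 80% requirement. Item 3 should therefore be settled together with item 1.
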